11.10.7 Confirmation Measurement

Confirmation of CR and PR is required and must occur no fewer than 4 weeks after initial documentation of CR or PR. If CR is pending confirmation and is designated at an assessment followed by 1 or more NE assessments, and/or PR assessments such that the Target Lesion Response is CR and the Non-Target Lesion Response is NE, CR may be confirmed thereafter if Non-Target Lesion Response returns to CR. Similarly, if a PR is pending confirmation and is designated at an assessment followed by 1 or more NE and/or SD assessments, PR may be confirmed thereafter. Subsequent Target Lesion Responses following a CR are limited to CR, PD or NE; PD for target lymph nodes is met only if any lymph node target lesion reaches a short axis measurement of ≥ 15 mm.

11.11 Appendix 11. Specific Guidance for Cytokine Release Syndrome, Immune-effector Cell-associated Neurologic Syndrome, and Tumor Lysis Syndrome

11.11.1 Specific Guidance for Cytokine Release Syndrome

Cytokine release syndrome (CRS) is defined as a supraphysiologic response following any immune therapy that results in the activation or engagement of endogenous or infused T-cells and/or other immune effector cells. Symptoms can be progressive, must include fever at the onset, and may include hypotension, capillary leak (hypoxia) and end organ dysfunction.

Clinical signs and symptoms of CRS are non-specific and may include a combination of the following:

- constitutional: fever \pm rigors, malaise, fatigue, anorexia, myalgias, arthralgias, nausea, vomiting, headache
- skin: rash
- gastrointestinal: nausea, vomiting, diarrhea
- respiratory: tachypnea, hypoxemia
- cardiovascular: tachycardia, widened pulse pressure, hypotension, increased cardiac output (early), potentially diminished cardiac output (late)
- coagulation: elevated D-dimer, hypofibrinogenemia \pm bleeding
- renal: azotemia
- hepatic: transaminitis, hyperbilirubinemia

The symptoms associated with the CRS event do not meet the definition of an adverse event as defined in Section 11.4. Therefore, the CRS associated event (ie, CRS, cytokine storm) should be documented on the Events electronic eCRF as the diagnosis. However, since it is important to document all symptoms related to a CRS event, a CRS Symptoms eCRF will also be available to record the symptoms associated with each CRS event.

If the severity of a CRS event changes from the date of onset to the date of resolution, record a single event for each increased level of severity on the Events eCRF and fill out an associated CRS Symptoms eCRF. If the symptoms worsen enough to impact the overall CRS grade, it is important to remember to record a new CRS event on the Events eCRF with the appropriate grade.

Temperature may normalize within a few hours of treatment, whereas the other components of CRS take longer to resolve. Once such therapies are used, the patient is

considered to still have CRS, even in the absence of fever, until all signs and symptoms leading to the diagnosis of CRS have resolved. Likewise, CRS can be downgraded in an afebrile patient treated with anticytokine therapy as their hemodynamic status and/or hypoxia improves. Typically, a patient with severe CRS in whom fever, oxygen, and pressor requirements have resolved may be assumed to have resolved CRS unless there are alternative causes for the fever, hypoxia, and/or hypotension.

Refer to [Table 6-2](#) for details regarding CRS grading and management.

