^d CRS grade is determined by the more severe event: hypotension or hypoxia not attributable to any other cause. For example, a subject with temperature of 39.5°C , hypotension requiring 1 vasopressor, and hypoxia requiring low-flow nasal cannula is classified as grade 3 CRS.

^e Low-flow nasal cannula is defined as oxygen delivered at ≤ 6 L/minute. Low-flow also includes blow-by oxygen delivery, sometimes used in pediatrics. High-flow nasal cannula is defined as oxygen delivered at > 6 L/minute.

^f For neutropenia adverse events grade ≤ 2 , please follow institutional guidelines for management.

For all other treatment interruptions or delays, restart tarlatamab in accordance with the following guidelines in [Table 6-3](#):

Table 6-3. Step dose Rechallenge Requirement After Tarlatamab Delay

Last Dose Administered	Duration of Delay from the Last Dose Administered	Action
Step dose (1 mg)	≤ 14 days	Proceed with tarlatamab 10 mg target dose and then continue treatment Q2W.
	> 14 days	Repeat tarlatamab 1 mg step dose per cycle 1 guidelines, including pre-medication and monitoring requirements (refer to Table 6-1).
First target dose (10 mg)	≤ 21 days	Proceed with tarlatamab 10 mg target dose and then continue treatment Q2W.
	> 21 days	Repeat tarlatamab 1 mg step dose schedule per cycle 1 guidelines, including pre-medication and monitoring requirements (refer to).
Any subsequent target dose (10 mg)	≤ 28 days	Proceed with tarlatamab 10 mg target dose and then continue treatment Q2W.
	> 28 days	Repeat tarlatamab 1 mg step dose per cycle 1 guidelines, including pre-medication and monitoring requirements (refer to Table 6-1).

Q2W = every 2 weeks.

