9.2 Sample Size Determination

Approximately 30 subjects will be enrolled in the study. With 30 subjects enrolled at the target dose, the probability that the observed ORR will be greater than **different thresholds are presented in Table 9-1.**

Table 9-1. Probabilities of Observed ORR Greater Than Thresholds With Sample Size of 30

True ORR	Probability of Observed ORR > 25 %	Probability of Observed ORR > 30%
0.35	88%	64%
0.4	96%	82%

ORR = overall response rate

With 30 subjects, there is a 79% to 96% probability of observing at least 1 adverse event if the true event rate is 5% to 10%.

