Both Amgen and the investigator reserve the right to terminate the investigator's participation in the study according to the Clinical Trial Agreement. The investigator is to notify the external review body in writing of the study's completion or early termination and send a copy of the notification to Amgen.

Subjects may be eligible for continued treatment with Amgen investigational product(s) by a separate protocol or as provided for by the local country's regulatory mechanism. However, Amgen reserves the unilateral right, at its sole discretion, to determine whether to supply Amgen investigational product(s) and by what mechanism, after termination of the study and before the product(s) is/are available commercially.

Compensation

Any arrangements for compensation to subjects for injury or illness that arises in the study are described in the Compensation for Injury section of the Informed Consent that is available as a separate document.

11.4 Appendix 4. Safety Events: Definitions and Procedures for Recording, Evaluating, Follow-up and Reporting

Definition of Adverse Event

Adverse Event Definition

 An adverse event is any untoward medical occurrence in a clinical study subject irrespective of a causal relationship with the study treatment. Note: An adverse event can therefore be any unfavorable and unintended sign (including an abnormal laboratory finding), symptom, or disease (new or exacerbated) temporally associated with the use of a treatment, combination product, medical device, or procedure. Note: Treatment-emergent adverse events will be defined in the Statistical Analysis Plan.
Events Meeting the Adverse Event Definition

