11.7.2 Reporting Criteria

Cases with events of elevation of AST, ALT, TBL, INR, mentioned above require the following:

- The event is to be reported to Amgen as a serious adverse event immediately and no later than 24 hours of discovery or notification of the event (ie, before additional etiologic investigations have been concluded).
- The appropriate case report form (CRF) (eg, Events electronic case report form (eCRF)) that captures information necessary to facilitate the evaluation of treatment-emergent liver abnormalities is to be completed and sent to Amgen.

Other events of **potential** hepatotoxicity are to be reported as serious adverse events if they meet the criteria for a serious adverse event defined in [Section 11.4](#).

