11.7.3.1.1 Important Alternative Causes

Important alternative causes for elevated AST/ALT and/or TBL values include, but are not limited to:

- hepatobiliary tract disease
- viral hepatitis (eg, hepatitis A/B/C/D/E, Epstein-Barr Virus, cytomegalovirus, herpes simplex virus, varicella, toxoplasmosis, and parvovirus)
- right-sided heart failure, hypotension or any cause of hypoxia to the liver causing ischemia.
- exposure to hepatotoxic agents/drugs or hepatotoxins, including herbal and dietary supplements, plants and mushrooms.
- heritable disorders causing impaired glucuronidation (eg, Gilbert's syndrome, Crigler-Najjar syndrome) and drugs that inhibit bilirubin glucuronidation (eg, indinavir, atazanavir)
- alpha-one antitrypsin deficiency
- alcoholic hepatitis
- autoimmune hepatitis
- Wilson's disease and hemochromatosis
- NASH (nonalcoholic fatty liver disease aka MASH) including steatohepatitis.
- non-hepatic causes (eg, rhabdomyolysis, hemolysis)

Special consideration is warranted when using products known to cause transient elevation of liver enzymes, such as T cell engager molecules. For example, in the instances of cytokine release syndrome (CRS) following exposure to BiTE molecules, transient elevations of isolated liver parameters were frequently noted.

Careful monitoring of laboratory parameters and the clinical status of subjects is required, and continuation of the medication may be considered and will be at the discretion of the investigators.

11.7.4 **Rechallenge and Dose Modification in Patients with Suspected Hepatotoxicity in Oncology Trials**

- The decision to rechallenge the subject is to be discussed and agreed upon unanimously by the subject, investigator, and Amgen. **If rechallenge is considered appropriate, the subject must be fully informed about the risk and should give written consent. Any rechallenge must be accompanied by close monitoring, with at least weekly liver biochemistry until response to the rechallenge is fully characterized.**
- If signs or symptoms recur with rechallenge, then Amgen investigational product and noninvestigational product(s)/auxiliary medicinal product(s), as appropriate is to be permanently discontinued. Subjects who clearly meet the criteria for permanent discontinuation are never to be rechallenged.

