9.6.2 Adverse Events

The Medical Dictionary for Regulatory Activities (MedDRA) version 27.0 or later is used to code all events categorized as adverse events to a system organ class and a preferred term.

The subject incidence of adverse events will be summarized for all TEAEs, TRAEs, serious TEAEs, grade 3 or higher TEAEs, fatal TEAEs, TEAEs leading to withdrawal of tarlatamab, TEAEs leading to interruption and/or reduction of tarlatamab. Subject incidence summary by system organ class and preferred term in descending order of frequency will be provided for all TEAEs, TRAEs, serious TEAEs, grade 3 or higher TEAEs, fatal TEAEs, TEAEs leading to withdrawal of tarlatamab, TEAEs leading to interruption and/or reduction of tarlatamab. Where appropriate the summary will also be provided by worst grade. Above summaries will not be created if two or fewer subjects experience the AE, subject-level data may be provided instead.

Severity of CRS and ICANS events will be graded using American Society for Transplantation and Cellular Therapy (ASTCT) (Lee et al, 2019) criteria. Severity of tumor lysis syndrome (TLS) will be graded using CTCAE version 5.0 but will be managed based on Cairo Bishop criteria ([Coiffier et al, 2008](#)). Severity of all other adverse events will be graded using CTCAE version 5.0.

Subject incidence of events of interest (standardized MedDRA queries and/or Amgen Medical Queries) will also be summarized according to their categories and preferred term if appropriate.

Adverse Events of Interest (EOI):

The summary of subject incidence of treatment-emergent adverse events of interest standardized MedDRA queries and/or Amgen Medical Queries such as cytokine release syndrome, hypersensitivity, immune effector cell associated neurotoxicity syndrome (ICANS) and associated neurological events, neutropenia, and neurological events will be summarized. The summary will include grade \geq 2, grade \geq 3, grade \geq 4, serious, fatal, and events leading to interruption and/or reduction and discontinuation of IP.

The subject incidence of above treatment-emergent EOIs, serious treatment-emergent EOI, grade 3 or higher treatment-emergent EOI, fatal treatment-emergent EOI, treatment-emergent EOI leading to discontinuation of investigational product and treatment-emergent EOI leading to interruption and/or reduction of

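### Section 11.11.1 says CRS symptoms are not adverse events, contrary to Section 11.4, so organ toxicity within CRS can lose its own term and CTCAE grade in the adverse event tables

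*Protocol*

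**What the plan says.** Protocol Section 11.11.1 gives a list of CRS signs and symptoms that goes beyond fever, hypotension and hypoxia. It includes hypofibrinogenemia with or without bleeding, azotemia, raised transaminases and bilirubin, and late reduction in cardiac output. It continues: "The symptoms associated with the CRS event do not meet the definition of an adverse event as defined in Section 11.4". On that ground CRS is entered on the Events eCRF as the diagnosis, and the symptoms go on a separate CRS Symptoms eCRF.

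The definition it points to, in Section 11.4, says an adverse event can be "any unfavorable and unintended sign (including an abnormal laboratory finding), symptom, or disease (new or exacerbated" (the parenthesis closes there) when associated in time with treatment. Section 11.4 also lists clinically significant abnormal laboratory results as adverse events. Separately, under recording, it tells the investigator to document the diagnosis and not its individual signs and symptoms.

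Table 6-2, footnote d, fixes the grade: "CRS grade is determined by the more severe event: hypotension or hypoxia not attributable to any other cause". SAP Section 9.6.2 follows: "Severity of CRS and ICANS events will be graded using American Society for Transplantation and Cellular Therapy (ASTCT" criteria).

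For liver values meeting Section 11.7.1, Section 11.7.2 says: "The event is to be reported to Amgen as a serious adverse event immediately and no later than 24 hours of discovery", before the cause has been worked out. Section 8.4.3 treats laboratory changes that need treatment or a change in therapy as adverse events.

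**The concern.** The sentence confuses two things. Recording a syndrome under one diagnosis is ordinary practice and Section 11.4 provides for it. Declaring that the components are not adverse events is different, and Section 11.4 contradicts it.

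The difference matters because the CRS grade cannot stand in for the severity of the organ findings listed as part of CRS. A liver, renal or bleeding finding does not move the grade at all, and cardiac dysfunction moves it only if it shows as hypotension or hypoxia. A site that follows 11.11.1 literally can enter a severe organ toxicity under a low-grade CRS term. The toxicity then has no row under its own preferred term, and it does not count as grade 3 or higher on its own account.

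Incidence of treatment-emergent adverse events is the safety endpoint (secondary, Section 3). In a trial where "Approximately 30 subjects will be enrolled in the study", one or two cases in a preferred-term row change what a reader concludes. Sites also receive conflicting instructions, so identical cases may be recorded differently.

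**Working it through.** **1. Definition against sentence.** The components listed in 11.11.1 are signs, symptoms and laboratory findings. Section 11.4 names exactly those as adverse events. The sentence's stated reason is therefore wrong. Its operative instruction, to enter CRS as the diagnosis, agrees with the recording rule in 11.4.

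**2. Does the grade carry the severity?** Inputs to the CRS grade in Table 6-2 are fever, hypotension and hypoxia. Two hypothetical cases, both febrile with neither hypotension nor hypoxia:
- *ALT above 3 x ULN and CTCAE grade 3.* CRS grade 1. Under 11.11.1 the ALT rise is not an adverse event. Under 11.7.1, ALT above 3 x ULN with fever meets a criterion where no other cause has been identified, and 11.7.2 then requires a serious adverse event report. Section 11.7.3.1.1 adds that in CRS after BiTE exposure "transient elevations of isolated liver parameters were frequently noted", so a site may treat CRS as the other cause. The two instructions are not reconciled.
- *A severe bleed.* CRS grade 1. No liver rule applies and no laboratory table displays the bleed. It goes on the CRS Symptoms eCRF; whether it is also entered as its own event is not stated.

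Section 11.11.1 asks for a new CRS record only when the CRS grade changes, so worsening organ toxicity at a constant CRS grade triggers none. For ICANS the protocol does address findings outside the grade: Table 11-7, footnotes d and e, allows them to be graded by CTCAE. CRS has no such provision.

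**3. What the other outputs recover.**
- Laboratory shift tables (Protocol 9.4.2.3.2; SAP 9.6.4): unscheduled values are included, but the SAP limits them to selected, unnamed parameters. Table 1-1 schedules no laboratory tests on C1D2 or C1D9, the days after the two infusions that Section 4.4 links most often to CRS.
- Hy's Law summary (SAP 9.6.4): one specific liver pattern.
- Bleeding and cardiac findings: D-dimer and fibrinogen are not in Table 11-1, and SAP 9.6.7 plans no ECG analysis.
- CRS Symptoms eCRF: the SAP names it only as a source of the last-known-alive date (SAP 5.1). No summary is planned.

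**4. How many subjects the rule covers.** Section 4.4 gives CRS at 10 mg in Study 20200491 as 40/133 grade 1, 27/133 grade 2 and 1/133 grade 3. Assuming those rates apply here:
- grade 1-2: 30 x (40 + 27)/133 = 30 x 0.504 = 15.1 subjects
- grade 3: 30 x 1/133 = 0.2 subjects

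The documents give no rate of severe organ toxicity within CRS, so the number of cases affected cannot be derived.

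**5. Link to the plan's own detection figure.** Section 9.2 states 79% to 96% for seeing at least one event at true rates of 5% to 10%. This reproduces: 1 - 0.95^30 = 78.5% and 1 - 0.90^30 = 95.8%. For an organ toxicity, that figure presumes each case is coded as its own event. If a share f is recorded under CRS instead, the chance of at least one separately coded case is 1 - (1 - p(1 - f))^30. The value of f is an assumption, so this is illustration only:

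| f | p = 5% | p = 10% |
|---|---|---|
| 0 | 78.5% | 95.8% |
| 25% | 68.2% | 90.4% |
| 50% | 53.2% | 78.5% |
| 75% | 31.4% | 53.2% |

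**The case against.** The strongest reply is that the sentence is only a clumsy reason for a sound instruction. Section 11.4 itself says to record the diagnosis, and 11.11.1 does not forbid a separate entry for a distinct complication. Section 11.4 also calls complications arising during hospitalization adverse events. Liver cases have their own serious-event route, treated laboratory changes are adverse events under 8.4.3, and laboratory shifts and Hy's Law cases are tabulated whatever the event coding. The study is descriptive, with no hypothesis tested.

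Most of this stands, and it rules out a stronger reading. A reader might infer that severe organ toxicity will be tabulated solely as grade 1-2 CRS and entered nowhere else. The documents do not support that, because the routes above exist and the CRS event may itself be grade 3-4. Nor are seriousness, relatedness and action taken lost: Section 11.4 makes them mandatory for every recorded event, CRS included, and SAP 9.6.2 tabulates serious and fatal events of interest and those leading to interruption or discontinuation.

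The reply does not remove the contradiction with 11.4, or the fact that CRS tables cannot show which organ was affected or how severely. The recovery routes are mainly laboratory ones, and the liver route depends on no other cause having been identified.

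**Conclusion.** The point holds in a limited form. Section 11.11.1 misstates Section 11.4 and conflicts with 11.7.2 and 8.4.3. Followed literally, it can leave hepatic, renal, bleeding or cardiac toxicity in the adverse event tables only under a lower-grade CRS term. What is lost there is the organ-specific preferred term and its CTCAE grade. The loss is partly recovered for laboratory findings and least recovered for bleeding and cardiac findings.

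About 15 of 30 subjects would have grade 1-2 CRS, on the assumption that Study 20200491 rates carry over. That is the number to whom the rule would apply, not a count of misrecorded events. A reader might go on to say how many subjects are missing from the grade 3 or higher table. That would need a rate of severe organ toxicity within CRS, which the documents do not give. It would also have to assume that no other route captures the case and that the subject has no other grade 3 or higher event. The overall incidence of any treatment-emergent event is unaffected.

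**What to change.** **Protocol 11.11.1.** Replace the sentence with the recording rule from 11.4: CRS is entered as the diagnosis, with its symptoms on the CRS Symptoms eCRF. Then state that an organ toxicity within CRS that the CRS grade does not reflect is also entered on the Events eCRF with its own CTCAE grade if it is CTCAE grade 3 or higher, is serious, or meets 11.7.1. This reconciles 11.11.1 with 11.4, 8.4.3 and 11.7.2.

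**SAP 9.6.2.** Include these events in the treatment-emergent tables. Add one summary of CRS Symptoms eCRF terms, by worst grade only if that form collects a grade; the documents do not say whether it does.

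**Cost.** Guidance wording and one table from data already collected. Some preferred-term counts rise slightly, and a CRS case and its organ toxicity appear in separate rows. The change concerns recording and analysis only; no dose, monitoring or treatment rule is touched.

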11.11.2 Specific Guidance for Immune-effector Cell-associated Neurologic Syndrome

For this trial, immune-effector cell associated neurologic syndrome (ICANS) will be using the criteria referenced in the publication by Lee et al, 2019. While the grading system has been developed in large part from chimeric antigen receptor T-cells (CAR-T) therapies, symptoms of ICANS may be shared among immune effector-cell associated therapies such as bispecific T-cell engager (BiTE[®]) molecules. Although there may be a wide range of symptoms associated with ICANS, subjects may have a stereotypic course of a specific set of symptoms. The earliest manifestations of ICANS are tremor, dysgraphia, mild difficulty with expressive speech (especially in naming objects), impaired attention, apraxia, and mild lethargy.

Immune-effector cell associated neurologic syndrome grade is determined by the most severe event (eg, depressed level of consciousness, seizure, motor findings, raised intracranial pressure [ICP]/cerebral edema) not attributable to any other cause. Refer to the immune-effector cell-associated encephalopathy (ICE) score below for grading of ICANS.

Immune-effector Cell-associated Encephalopathy (ICE) Assessment Tool

- Orientation: Orientation to year, month, city, hospital: 4 points
- Naming: ability to name 3 objects (eg, point to clock, pen, button): 3 points
- Following commands: ability to follow simple commands (eg, "Show me two fingers" or "Close your eyes and stick out your tongue"): 1 point
- Writing: ability to write a standard sentence (eg, "Our national bird is the bald eagle"): 1 point
- Attention: ability to count backwards from 100 by 10: 1 point

ICE scoring

- 7 to 9, grade 1
- 3 to 6, grade 2
- 0 to 2, grade 3
- 0 due to subject unarousable and unable to perform ICE
- Assessment, grade 4

Table 11-7. ASBMT Immune-effector Cell-associated Neurotoxicity Syndrome (ICANS) Consensus Grading for Adults

Neurotoxicity Domain ^a	Grade 1	Grade 2	Grade 3	Grade 4
ICE score ^b	7-9	3-6	0-2	0 (subject is unarousable and unable and unable to perform ICE)
Depression level of consciousness ^c	Awakens spontaneously	Awakens to voice	Awakens only to tactile stimulus	Subject is unarousable or requires vigorous or repetitive tactile stimuli to arouse. Stupor or coma
Seizure	N/A	N/A	Any clinical seizure focal or generalized that resolves rapidly or nonconvulsive seizures on EEG that resolve with intervention	Life-threatening prolonged seizure (> 5 min); or repetitive clinical or electrical seizures without return to baseline in between
Motor findings ^d	N/A	N/A	N/A	Deep focal motor weakness such as hemiparesis or paraparesis
Elevated ICP/cerebral edema	N/A	N/A	Focal/local edema on neuroimaging ^e	Diffuse cerebral edema on neuroimaging; Decerebrate or decorticate posturing; or Cranial nerve VI palsy; or Papilledema; or Cushing's triad

ASBMT = American Society for Blood and Marrow Transplantation; CTCAE = Common Terminology Criteria for Adverse Events; EEG = electroencephalogram; ICANS = immune-effector cell associated neurologic syndrome; ICE = immune-effector cell-associated encephalopathy; ICP = intracranial pressure;

N/A = not applicable

^a Other signs and symptoms such as headache, tremor, myoclonus, asterixis, and hallucinations may occur and could be attributable to immune effector-cell engaging therapies. Although they are not included in this grading scale, careful attention and directed therapy may be warranted.

^b A subject with an ICE score of 0 may be classified as grade 3 ICANS if awake with global aphasia, but a subject with an ICE score of 0 may be classified as grade 4 ICANS if unarousable.

^c Depressed level of consciousness should be attributable to no other cause (eg, no sedating medication).

^d Tremors and myoclonus associated with immune effector cell therapies may be graded according to CTCAE v5.0, but they do not influence ICANS grading.

^e Intracranial hemorrhage with or without associated edema is not considered a neurotoxicity feature and is excluded from ICANS grading. It may be graded according to CTCAE v5.0.

Source: Lee et al, 2019

Assessment and Supportive Care Recommendations (all grades)

- Neurologic assessment and grading at least twice a day to include cognitive assessment and motor weakness

- MRI of the brain with and without contrast (or brain CT if MRI is not feasible) for \geq grade 2 neurotoxicity
- Neurology consultation at first sign of neurotoxicity
- Conduct electroencephalogram (EEG) for seizure activity for \geq grade 2 neurotoxicity
- Aspiration precautions; IV hydration
- Use caution when prescribing medications that can cause central nervous system (CNS) depression (aside from those needed for seizure prophylaxis/treatment)

